#### 6.4.3.9 Mortality Rate

The analysis of this endpoint will be performed on the ITT population. The number and percentage of patients who died will be presented. The percentage of patients who died will be compared using a binary logistic regression. The model will include only the treatment group. Contrasts under this model will allow for the comparisons across treatment groups. The results will be presented as odds ratios, with associated 80% CIs and p-values. The period will cover from the time of randomization to 28 days after, any death for which date of death > date of randomization + 28 would be excluded.

A listing with details on deaths will be provided (Section 7, Listing 10).

#### 6.4.4 Sensitivity Analysis

As a sensitivity analysis, the primary analysis described in section 6.4.1 will be repeated on the PP population.

As an additional sensitivity analysis, the primary endpoint will be derived using the algorithm of Appendix 1, but prior to applying the algorithm, the last observation carried forward will be used in alive patients with no assessment at Day 28. In other words, in alive patients, the missing assessment at Day 28 will be imputed as the last available assessment.

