### 6 STATISTICAL METHODOLOGY

#### 6.1 Determination of Sample Size

As per protocol, it was anticipated that 208 patients will be randomized into the study in a 1:1:1:1 ratio to 900, 1800, or 3600 mg dalcetrapib or placebo. The original sample size was calculated for the sustained resolution endpoint and was described in the protocol as follows: The purpose of the proof-of-concept study is to identify whether there is sufficient promise of efficacy to justify conducting a Phase 3 study in a larger sample size and to determine efficacious dose to be used in Phase 3. While the entirety of data will be considered at the end of study, the sample size has been chosen to ensure that a positive trend will be present with alpha of 0.2 when considering the two highest doses combined compared to placebo. One-hundred twenty-seven (127) resolution events provides 80% power to demonstrate a positive trend if the average hazard ratio (HR) of the two dalcetrapib groups is 1.4 relative to placebo. Allowing for 20% of patients not resolving, 156 patients (52 per treatment arm) will be enrolled across the two highest dose levels and placebo arms, and an additional 52 will be randomized to 900 mg for a total sample size of 208 patients.

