##### **6.4.1 Primary Analysis**

The primary endpoint is time to sustained clinical resolution of symptoms (excluding cough, sense of smell and taste) as determined by symptom score. Sustained clinical resolution of symptoms (excluding cough, sense of smell and taste) is defined in Section 4.1. Time to sustained clinical resolution will be calculated as date of resolution – date of randomization + 1. Subjects who did not resolve will be censored at the last time point where they were not resolved [see Section 9 Appendix 1]. The number and percentage of patients whose symptoms resolved will be presented, and to summarize the time to resolution, censored subjects will be imputed with a time to resolution of 29 days and simple medians with 80% confidence intervals will be provided.

The differences in time to sustained clinical resolution of symptoms (excluding cough, sense of smell and taste) between the treatment groups will be evaluated using 2-sided log-rank tests. The combined two highest treatment groups will be compared to placebo in addition to the comparison of individual doses.

The cumulative incidence curve for sustained clinical resolution (excluding cough, sense of smell and taste) will also be presented using 1 – Kaplan-Meier estimates(Section 7, Figure 2). Should there be several deaths, the cumulative incidence curve will be presented under a competing risk model.

A listing with the score of each symptom at each time point will be provided (Section 7, Listing 7).

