## 9 APPENDICES

### APPENDIX 1

Algorithm used to classify sustained clinical resolution:

For each subject, all ePRO records will be sorted by the date/time. For each assessment, we characterize the record as clinically resolved (i.e., score of 0 for taste and smell and all other symptoms, a score of 0 or 1) or not.

From Day1 to Day10 (or last ePRO assessment before Day14)

- a) If resolved at Day 10 (or last ePRO assessment), identify first date when resolution occurred with no relapse. This is the tentative date of resolution to be confirmed at Day 14 and Day 28.
- b) If not resolved at Day 10 (or last ePRO assessment), re-assess at Day 14.

At Day14:

- c) If resolved for the first time at Day 14 (i.e. was not resolved at Day 10 or before), use date of Day 14 as the tentative date of resolution to be confirmed at Day 28.
- d) If still resolved at Day 14 (i.e. was already resolved at Day10 or before), use date of resolution identified in step a). This is the tentative date of resolution to be confirmed at Day 28.
- e) If not resolved at Day 14, re-assess at Day28.

At Day28:

- f) If resolved for the first time at Day 28 (i.e., was not resolved at Day 14), subject will be classified as resolved within 28 days and date of resolution will be the date of Day 28.
- g) If still resolved at Day 28 (i.e. was already resolved at Day 14), subject will be classified as resolved within 28 days and date of resolution will be the date of resolution identified in step c) or d).
- h) If not resolved at Day 28, subject will be classified as not resolved within 28 days and the date of censoring will be the date of Day 28.

It should also be noted that subjects who do not have an assessment at Day 28 will be classified as non-resolved REGARDLESS if symptoms were resolved up to their last assessment. Date of censoring will be the date of study discontinuation.

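### The Day 28 LOCF sensitivity analysis keeps patients who left unresolved in the log-rank risk set to Day 28, so it can be biased when unresolved dropout differs by arm

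*SAP*

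**What the plan says.** **Primary rule.** Under the last paragraph of SAP Appendix 1, patients with no Day 28 assessment "will be classified as non-resolved REGARDLESS if symptoms were resolved up to their last assessment". Their log-rank time ends early: "Date of censoring will be the date of study discontinuation". SAP 6.4.1 words the censoring point differently: "Subjects who did not resolve will be censored at the last time point where they were not resolved". For the summary of times, "censored subjects will be imputed with a time to resolution of 29 days and simple medians with 80% confidence intervals will be provided". Group differences "will be evaluated using 2-sided log-rank tests", and SAP 6.2 sets a two-sided 0.20 level.

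**Sensitivity rule.** SAP 6.4.4 fills the gap before Appendix 1 is run: "in alive patients, the missing assessment at Day 28 will be imputed as the last available assessment". A patient with an unresolved Day 28 value then meets step h: "subject will be classified as not resolved within 28 days and the date of censoring will be the date of Day 28".

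**Other checks.** The only other sensitivity analysis in SAP 6.4.4 repeats the primary analysis in the per-protocol population. That leaves the missing-data rule as it is.

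**The concern.** On a recovery endpoint, carrying an unresolved score forward assumes that the patient did not recover. Someone who left unresolved on Day 5 gains 28 - 5 = 23 days of event-free follow-up that nobody observed. If more such patients leave one arm, that arm's risk sets are inflated and its hazard ratio (HR) for resolution is pulled down, even when recovery is the same in both arms.

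This is the only planned check on missing Day 28 data for the primary endpoint. A biased check could cast doubt on a sound primary result or appear to support a weak one.

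**Working it through.** **1. Inputs**
- From the documents: 1:1:1:1 allocation with 52 per arm, so the two highest doses v placebo are 104 v 52; design HR 1.4; two-sided 0.20 tests; scores on Days 1-10, 14 and 28; and, in SAP 6.1, "Allowing for 20% of patients not resolving".
- Assumed: exponential recovery, no relapse, and all dropout rates and timings.

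**2. The plan's own figure**
- Power-family spending (rho = 2) of a one-sided 0.2 at 73 of 127 events uses 0.2 × (73/127)² = 0.066. This gives an interim bound of HR 1.453.
- The final one-sided alpha is 0.186. Power at 127 events, with the futility stop at HR 1, is 80.0%. The protocol's design reproduces.
- The SAP now tests two-sided at 0.20, so an unbiased test gives a false result in each direction 10% of the time.

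**3. What each rule does to an alive patient with no Day 28 score**

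| Last seen | Item | Primary | LOCF |
|---|---|---|---|
| Unresolved | Resolved count | Not resolved | Not resolved |
| Unresolved | Value for median | 29 days | 29 days |
| Unresolved | Log-rank time | Censored at discontinuation | Censored at Day 28 |
| Resolved | Resolved count | Not resolved | Resolved |
| Resolved | Log-rank time | Censored at discontinuation | Event on tentative date |

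For unresolved leavers, only the log-rank time moves, and with it the cumulative incidence curve.

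**4. How far the carried value is from the plan's expectation**
- With 80% resolved by Day 28, the rate is -ln(0.2)/28 = 0.0575 per day.
- P(resolve by Day 28 | unresolved on Day k) = 1 - exp(-0.0575 × (28 - k)). This is 73% for k = 5 and 64% for k = 10. LOCF treats it as 0%.

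**5. Simulation of the log-rank test**

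There were 2,000 to 3,000 trials per setting; ranges show independent runs. Percentages are false unfavourable results unless stated. Dropout is active v placebo. The last column keeps observed resolutions and censors unresolved leavers at their last score.

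| Setting | LOCF | Primary | Censor at last score |
|---|---|---|---|
| No effect, 15% v 5%, Days 2-10 | HR 0.91-0.92, 23% | HR 0.96, 16% | HR about 1.0, 10-11% |
| No effect, 5% v 15%, Days 2-10 | HR 1.09-1.10, false favourable 22-23% | HR 1.04 | HR 0.99, false favourable 9-10% |
| HR 1.4, 15% v 5%, Days 2-10 | HR 1.20, power 40-41% | HR 1.26, power 53% | HR 1.33, power 67-68% |
| HR 1.4, 15% in both arms, Days 2-10 | Power 59-61% | Power 63% | Power 65-66% |
| No effect, 8% v 5% | HR 0.97, 13% | 11% | Not reported |
| No effect, 15% v 5%, Days 2-27 | HR 0.95, 17-20% | HR 0.92, 21-22% | HR near 1.00 |
| No effect, 15% v 5%, Days 10-27 | HR 0.96, 15% | HR 0.91, 24% | HR near 1.00 |

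The true 1.4 reads as about 1.33 because visits are sparse after Day 10.

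**6. Who leaves matters**

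A second model with no effect and 20% v 10% leaving, where the last column is ordinary censoring that keeps observed resolutions, gave these HRs:

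| Leavers | LOCF | Primary | Ordinary censoring |
|---|---|---|---|
| At random | 0.92 | 0.89 | 0.99 |
| Only unresolved patients | 0.82 | 0.95 | 0.95 |
| Only resolved patients | 0.99 | 0.88 | 0.99 |

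**The case against.** Several stronger readings are tempting, and the documents do not support them.

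- **LOCF turns unresolved leavers into failures.** The primary already classes them as not resolved and sets them to 29 days for the medians. Only the log-rank censoring date moves.
- **It is biased whenever dropout differs by arm.** When the extra leavers had already resolved, LOCF gave HR 0.99. Nor would there be bias if they would not have resolved by Day 28 anyway.
- **It is worse than the primary.** That holds for early leaving. With leaving spread over follow-up, LOCF is the less biased of the two, because it credits leavers last seen resolved, whom the primary counts as not resolved.
- **It cannot show robustness.** Any change in the resolved count between Tables 2.1.1 and 2.1.3 comes only from leavers last seen resolved. The analysis therefore does test the primary's most questionable rule. Only its log-rank result mixes the two changes.

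Further objections have weight. No dropout rate is stated, and Protocol 4.4.5 asks patients who withdraw to complete the remaining procedures, so little may be missing. The 20% allowance was set for the protocol's endpoint. The SAP primary endpoint drops cough, smell and taste, which can only make resolution easier, so 80% is if anything low. SAP 6.4.4 imputes a score and does not mention a date. A programmer could keep the discontinuation date, and then no event-free time would be added. However, once a Day 28 score exists, the paragraph on missing Day 28 assessments no longer applies and step h names Day 28, so the reading used here is the natural one.

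**Conclusion.** The concern holds in this limited form: as written, the LOCF check can be biased in its log-rank test and cumulative incidence curve when unresolved dropout differs by arm. With an effect present, it can also lose power at equal dropout.

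In the early-leaving case (15% v 5%, Days 2-10, no effect), false unfavourable results are about 23%, against 16% for the primary itself and 10-11% when unresolved leavers are censored at their last score. The fair increment over the planned primary is therefore about 7 percentage points, not 13. With leaving spread over follow-up, LOCF is still biased but slightly less than the primary (HR about 0.92-0.95 v 0.89-0.92). At 8% v 5% the bias is small.

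These sizes rest on assumed dropout, exponential recovery, no relapse and the step h reading. The analysis remains informative about leavers last seen resolved. The change is worth making because it costs little, but it concerns one sensitivity analysis in an exploratory Phase 2a trial.

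**What to change.** Reword SAP 6.4.4 for alive patients with no Day 28 assessment:
1. If resolved at the last assessment, count as resolved on the tentative date from Appendix 1 step a, c or d.
2. If not resolved at the last assessment, censor at the date of that assessment and carry nothing forward.

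Use this rule for Table 2.1.3 and for Figure 4 in the SAP Section 7 list. The LOCF version may stay as an additional analysis, labelled as a worst case for unresolved leavers, with its censoring date stated. At the same time, reconcile the primary censoring date between SAP 6.4.1 and Appendix 1.

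The cost is a few lines of SAP text and the programming of one table and one figure, with no new data. The downside is that the rule assumes leaving while unresolved is non-informative. When only unresolved patients left (20% v 10%), ordinary censoring itself gave HR 0.95. The rule also treats unresolved leavers much as the primary does, so it tests mainly the primary's handling of resolved leavers. Keeping the labelled LOCF version covers part of that gap.

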#### 6.4.5 Subgroup Analysis

A subgroup analysis for the variants might be done on the primary endpoint, time to sustained clinical resolution of symptoms (excluding cough, sense of smell and taste). The analysis described in section 6.4.1 would be repeated in subjects presenting a specific variant. These analyses would however be done at a later time point when the information on the variants become available.

### 6.5 Safety Analysis

The safety analyses described in this section will be conducted on the safety population. No formal statistical testing is planned for the safety parameters.

#### 6.5.1 Treatment Exposure

Duration of exposure will be defined as number of days on treatment for each subject. Duration will be calculated as: [treatment end date – treatment start date + 1] from the eCRF Form “Study Drug Administration”.

Duration of exposure will be summarized by treatment arm using N, mean, median, standard deviation, Q1, Q3, minimum and maximum.

Duration of exposure will also be categorized according to day intervals ([1-3], [4-5], [6-7], [8-9], [10], [>10]) and summarized using frequencies and percentages, overall and by treatment group.

In addition, if subject interrupted/discontinued the study medication, then the reason will also be reported using frequencies and percentages overall and by treatment group.

Duration of exposure will be presented for the safety population.

A listing with details on the administration of study medication will be provided (Section 7, Listing 6).

## **6.5.2 Adverse Events and Serious Adverse Events**

### **6.5.2.1 Adverse Events**

AEs will be coded by system organ class and preferred term according to the MedDRA dictionary (version 24).

Treatment-emergent AEs (TEAEs) will be summarized. Number and proportion of subjects experiencing a treatment-emergent AE will be presented by system organ class and preferred term overall and for each treatment group.

An overall summary of TEAEs that includes the total number of TEAEs reported, the number and proportion of subjects experiencing at least one TEAE, at least one severe TEAE, at least one TEAE related to the study treatment, at least one TEAE leading to treatment discontinuation and a TEAE leading to death will also be presented.

TEAEs related to study treatment will also be summarized. Number and proportion of subjects experiencing a treatment-emergent AE related to study treatment will be presented by system organ class and preferred term overall and for each treatment group.

An overall summary of TEAEs related to study treatment that includes the total number of TEAEs reported, the number and proportion of subjects experiencing at least one TEAE, at least one severe TEAE, at least one TEAE leading to treatment discontinuation and a TEAE leading to death will also be presented.

TEAEs leading to treatment discontinuation will also be summarized. Number and proportion of subjects experiencing a treatment-emergent AE leading to treatment discontinuation will be presented by system organ class and preferred term overall and for each treatment group. Severe TEAEs will be presented similarly.

All AEs will also be listed (Section 7, Listing 9).

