### **1.3. Risk-benefit Assessment**

Dalcetrapib is an oral, safe and generally well-tolerated drug which could target mild, moderate, and severe forms of the COVID-19, and possibly prevent COVID-19 in high-risk or exposed patients.

No obvious toxicity was observed in the in-vivo toxicity studies. The major dose-limiting finding associated with dalcetrapib in monkeys was gastrointestinal toxicity (diarrhea and loose stools). In general, dalcetrapib has been well-tolerated in patients with CHD. In the short-term (<12 weeks) Phase 1 and 2 studies, the incidence of adverse events (AEs) leading to discontinuation of dalcetrapib (300, 600, and 900 mg) was low across the Phase 1 healthy volunteer and Phase 2 patient studies. The majority of the AEs were of mild or moderate intensity. The most frequently reported AEs were those from body system organ classes of gastrointestinal system and nervous system, and included diarrhea, stool abnormalities, and headache.

More detailed information about the known and expected benefits and risks and reasonably expected adverse events of dalcetrapib may be found in the Investigator's Brochure.

As the study subjects targeted are patients with limited treatment options, the study supports further investigation of dalcetrapib in patients with mild to moderate symptoms due to COVID-19 in a Phase 2a setting.

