### **8.5. Safety Analysis**

Safety variables include incidence of AEs (or TEAEs), laboratory test results, and vital signs. All safety analyses will be based on the Safety Population. No formal statistical analysis of the safety data will be performed.

Adverse events will be coded according to MedDRA, version 23.0 released 19 Apr 2020 (exclusively meant for COVID-19) or later.

The number and percentage of patients with TEAEs, SAEs, TEAEs related to study treatment, SAEs related to study treatment, TEAEs leading to treatment discontinuation, TEAEs leading to study discontinuation, and TEAEs leading to death will be summarized by SOC, preferred term (PT), and treatment group. In addition, the severity of TEAEs and relationship to study treatment will be summarized by SOC, PT, and treatment group.

The AE summary tables will include counts of patients. Therefore, if a patient experiences more than 1 episode of a particular AE, the patient will be counted only once for that event. If a patient has more than one AE that is coded to the same PT, the patient will be counted only once for that PT. Similarly, if a patient has more than 1 AE within a SOC, the patient will be counted only once in that SOC.

Test values and change from baseline will be summarized descriptively by treatment group for specific laboratory test results and vital signs. Where applicable, shift tabulations will be presented for specific laboratory test results by treatment group. Where applicable, number and frequency of clinically significant abnormal values for specific laboratory test results will be presented.

Pregnancy test results and patients with confirmed positive pregnancy test result will be listed.

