### **Assessment of Severity**

The Investigator will be asked to provide an assessment of the severity of the AE using the following categories:

- **Mild:** Usually transient and may require only minimal treatment or therapeutic intervention. The event does not generally interfere with usual activities of daily living.
- **Moderate:** Usually alleviated with additional specific therapeutic intervention. The event interferes with usual activities of daily living, causing discomfort but poses no significant or permanent risk of harm to the patient.
- **Severe:** Interrupts usual activities of daily living, significantly affects clinical status, or may require intensive therapeutic intervention.

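### The SAP leaves out the protocol's breakdown of adverse-event severity by term and arm, so mild and moderate events are pooled and a mild-to-moderate shift at constant incidence would show in no table.

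*SAP*

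**What the plan says.** **Protocol.** Section 8.5 commits to a severity summary: "In addition, the severity of TEAEs and relationship to study treatment will be summarized by SOC, PT, and treatment group". The synopsis makes the same commitment twice, under its safety evaluation and its safety analysis. Appendix 1 sets up a three-grade scale of mild, moderate and severe: "The Investigator will be asked to provide an assessment of the severity of the AE using the following categories". The line it draws between mild and moderate is whether the event interferes with usual daily activities.

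**SAP.** Section 6.5.2.1 plans, by term and arm:
- all TEAEs of any grade (Table 3.2.2): "Number and proportion of subjects experiencing a treatment-emergent AE will be presented by system organ class and preferred term overall and for each treatment group";
- TEAEs related to study treatment (Table 3.2.4): "Number and proportion of subjects experiencing a treatment-emergent AE related to study treatment will be presented by system organ class and preferred term";
- TEAEs leading to treatment discontinuation (Table 3.2.5);
- severe TEAEs (Table 3.2.6): "Severe TEAEs will be presented similarly".

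Serious events follow in Tables 3.2.8 and 3.2.10. The overall summaries count patients with at least one severe event. All adverse events are listed in Listing 9, whose columns are not specified. The Section 7 table list contains no table by mild, moderate and severe.

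**Precedence.** SAP Section 1 says the SAP prevails where it differs from the protocol. Neither that section, which explains the changed emphasis in efficacy, nor the revision history gives a reason for dropping the severity breakdown.

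**The concern.** The safety objective in both documents is the safety and tolerability of the active doses compared with placebo. Protocol 1.3 says of the short-term studies at 300, 600 and 900 mg: "The majority of the AEs were of mild or moderate intensity". It names diarrhea, stool abnormalities and headache among the most frequent events. This trial also gives 1800 and 3600 mg. Protocol 3.4 reports drug exposure at doses up to 3900 mg but no tolerability by dose.

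If higher doses make events worse rather than more common, the first sign would be events moving from mild to moderate. The protocol's severity summary would show that directly. The SAP's tables cut the scale only between moderate and severe, so they do not. The trial is also meant "to determine efficacious dose to be used in Phase 3", and the by-arm safety tables will be read alongside that decision.

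**Working it through.** The plan states no figure on this point, so there is nothing to reproduce. The check has three steps.

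**1. What the tables identify.** For one preferred term in one arm:
- Table 3.2.2 gives patients with any grade, A.
- Table 3.2.6 gives patients with a severe event, S.
- A − S is the number whose worst grade was mild or moderate.

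No planned table splits A − S. Tables 3.2.4 and 3.2.5 add relatedness and discontinuation, not grade.

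**2. Which dose effects would show.** The documents give 52 patients per arm. All event rates below are assumptions.

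*Moderate events add to the total.* Mild is 10% throughout, and the severe rate is the same in both arms. Each count is 52 × rate.

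| Moderate, low v high | Severe | A, low v high | A − S, low v high |
|---|---|---|---|
| 5% v 15% | 0% | 7.8 v 13.0 | 7.8 v 13.0 |
| 5% v 20% | 2% | 8.8 v 16.6 | 7.8 v 15.6 |
| 5% v 25% | 2% | 8.8 v 19.2 | 7.8 v 18.2 |

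Table 3.2.2 shows the rise, without saying that it is moderate.

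*Events shift from mild to moderate with the total fixed.*

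| Any grade, both arms | Severe, both arms | A, both arms | S, both arms | Moderate, low v high |
|---|---|---|---|---|
| 20% | 0% | 10.4 | 0 | 5% v 15%: 2.6 v 7.8 |
| 30% | 2% | 15.6 | 1.0 | 5% v 20%: 2.6 v 10.4 |
| 40% | 2% | 20.8 | 1.0 | 10% v 30%: 5.2 v 15.6 |

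Tables 3.2.2 and 3.2.6 are the same in both arms. The shift is hidden.

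**3. Size of one hidden difference, for illustration.** Assume moderate diarrhea of 4% on placebo and 15% on 3600 mg (52 × 0.04 = 2.1 and 52 × 0.15 = 7.8 patients), with equal all-grade rates.
- Difference: 0.15 − 0.04 = 0.11.
- Standard error: √(0.04 × 0.96/52 + 0.15 × 0.85/52) = 0.0565.
- 80% interval: 0.11 ± 1.2816 × 0.0565, or about 0.04 to 0.18.

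The interval only gauges size, since neither document plans formal testing of safety data. For comparison, if the severe rate for one term is 1% or 2%, the chance that one arm shows no severe case is 0.99^52 = 0.59 or 0.98^52 = 0.35. This is for one term in one arm and says nothing about the whole of Table 3.2.6.

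**The case against.** **The SAP does not tabulate only severe events.** A reader might infer from the sentence on severe TEAEs that other grades are absent by term. They are not: Tables 3.2.2, 3.2.4 and 3.2.5 include them. This stands.

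**Moderate events are not invisible.** A reader might also infer that a dose-related rise in moderate events cannot be seen. If the rise adds patients, it shows in Table 3.2.2 and in the difference from Table 3.2.6. Only the constant-incidence shift is hidden, and nothing in the documents makes constant incidence likely across a fourfold dose range. This also stands, and it limits the point.

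**Other outputs bear on tolerability.** Discontinuations due to events, reasons for interrupting or stopping drug (SAP 6.5.1) and missed pills (SAP 6.3.5) are all summarized by arm. Listing 7 gives each symptom score, including headache and diarrhea. These are indirect signs. Listing 9 may carry the grade, but a listing of unspecified columns is not the by-arm summary the protocol promised.

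**Diarrhea and headache are qualifying COVID-19 symptoms.** Their grade as adverse events partly reflects the disease, so they are imperfect markers of a drug effect. True, although background disease also blurs the all-grade counts.

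**The layout is a matter of presentation.** The protocol prescribes no table format, and the SAP may override it. The SAP likewise reduces the four relatedness categories to two. That is fair, but for severity the chosen cut falls above the grades that Protocol 1.3 leads one to expect, and no reason is given.

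**Dose selection.** The quoted aim concerns an efficacious dose, and SAP Section 1 puts more weight on viral load. No section makes adverse-event grade a criterion for choosing the dose. A claim that the omission undermines the Phase 3 dose choice would go beyond the documents.

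**Conclusion.** The omission is real: the protocol promises severity by term and arm, the SAP delivers only the severe grade, and mild and moderate events are pooled in every planned table without explanation. The consequence is narrow. A shift from mild to moderate at roughly constant incidence would appear in no table as a change of grade, and could be recovered only by hand from Listing 9 if that listing records severity. A rise that increases total incidence would be seen.

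The patient counts and the 11-point example rest on assumed rates, and the example also assumes equal all-grade incidence. They show what could be missed, not what is expected. The documents give no severe rate, so they do not support saying that the severe table will be nearly empty.

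Priority is minor. No primary or key secondary inference is affected. The point bears on how fully the tolerability objective is reported.

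**What to change.** Expand Table 3.2.6 to TEAEs by worst severity (mild, moderate, severe), system organ class, preferred term and treatment group, with each patient counted once per term at the worst grade. Add the same table for treatment-related TEAEs. Amend SAP 6.5.2.1 and the Section 7 list to match, and keep both tables descriptive. If the sponsor prefers the severe-only table, the SAP should record the departure from Protocol 8.5 with its reason and state that Listing 9 carries severity.

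The cost is one expanded and one added table shell, using grades that the protocol already has investigators assign. The downside is longer tables.
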